## 11. MEASUREMENT OF EFFECT

## 11.1 Antitumor Effect – Solid Tumors

Response and progression will be evaluated in this study using the new international criteria proposed by the Response Evaluation Criteria in Solid Tumors (RECIST) guideline (version 1.1) [Eur J Ca 45:228-247, 2009]. Changes in the largest diameter (unidimensional measurement) of the tumor lesions and the shortest diameter in the case of malignant lymph nodes are used in the RECIST criteria.

Pembrolizumab, like other immunotherapeutic agents, may produce antitumor effects by potentiating endogenous cancer-specific immune responses. The response patterns seen with such an approach may extend beyond the typical time course of image responses seen with cytotoxic agents, and can manifest as a clinical response after an initial increase in tumor burden or even the appearance of new lesions.

For any subject who showed first radiologic evidence of progressive disease (PD) by RECIST 1.1 (see Section 11.1) and is deemed clinically stable, it is at the discretion of the investigator to continue treating the subject until progression is confirmed at the next scheduled restaging (or with a confirmatory completed at least 4 weeks from the initial date of PD). If progression is not confirmed on the subsequent scan, the subject should continue to receive treatment and have radiographic scans performed according to the study calendar [approximately every 3 cycles (9 weeks) for the first 12 months and then every 4 cycles (12 weeks)]. If radiologic progression is confirmed, then the subject should be discontinued from all study treatment. If the treating investigator feels that the participant is clinically stable, demonstrates improved condition, or is clearly continuing to benefit from the treatment; the PI may approve the participant to continue to receive study treatment. In all participants, the date of progression will be documented as the first date progression was observed.

### 11.1.1 Definitions

**Evaluable for Target Disease response.** Only those participants who have measurable disease present at baseline, have received at least one cycle of therapy, and have had their disease re-evaluated will be considered evaluable for target disease response. These participants will have their response classified according to the definitions stated below. (Note: Participants who exhibit objective disease progression prior to the end of cycle 1 will also be considered evaluable.)

**Evaluable Non-Target Disease Response.** Participants who have lesions present at baseline that are evaluable but do not meet the definitions of measurable disease, have received at least one cycle of therapy, and have had their disease re-evaluated will be considered evaluable for non-target disease. The response assessment is based on the presence, absence, or unequivocal progression of the lesions.

### 11.1.2 Disease Parameters

**Measurable disease.** Measurable lesions are defined as those that can be accurately measured in at least one dimension (longest diameter to be recorded) as  $\geq 20$  mm by

chest x-ray or  $\geq 10$  mm with CT scan, MRI, or calipers by clinical exam. All tumor measurements must be recorded in millimeters (or decimal fractions of centimeters).

Note: Tumor lesions that are situated in a previously irradiated area are not considered measurable.

Malignant lymph nodes. To be considered pathologically enlarged and measurable, a lymph node must be  $\geq 15$  mm in short axis when assessed by CT scan (CT scan slice thickness recommended to be no greater than 5 mm). At baseline and in follow-up, only the short axis will be measured and followed.

Non-measurable disease. All other lesions (or sites of disease), including small lesions (longest diameter  $< 10$  mm or pathological lymph nodes with  $\geq 10$  to  $< 15$  mm short axis), are considered non-measurable disease. Bone lesions, leptomeningeal disease, ascites, pleural/pericardial effusions, lymphangitis cutis/pulmonitis, inflammatory breast disease, abdominal masses (not followed by CT or MRI), and cystic lesions are all considered non-measurable.

Note: Cystic lesions that meet the criteria for radiographically defined simple cysts should not be considered as malignant lesions (neither measurable nor non-measurable) since they are, by definition, simple cysts.

'Cystic lesions' thought to represent cystic metastases can be considered as measurable lesions, if they meet the definition of measurability described above. However, if non-cystic lesions are present in the same participant, these are preferred for selection as target lesions.

Target lesions. All measurable lesions up to a maximum of 2 lesions per organ and 5 lesions in total, representative of all involved organs, should be identified as **target lesions** and recorded and measured at baseline. Target lesions should be selected on the basis of their size (lesions with the longest diameter), be representative of all involved organs, but in addition should be those that lend themselves to reproducible repeated measurements. It may be the case that, on occasion, the largest lesion does not lend itself to reproducible measurement in which circumstance the next largest lesion which can be measured reproducibly should be selected. A sum of the diameters (longest for non-nodal lesions, short axis for nodal lesions) for all target lesions will be calculated and reported as the baseline sum diameters. If lymph nodes are to be included in the sum, then only the short axis is added into the sum. The baseline sum diameters will be used as reference to further characterize any objective tumor regression in the measurable dimension of the disease.

Non-target lesions. All other lesions (or sites of disease) including any measurable lesions over and above the 5 target lesions should be identified as **non-target lesions** and should also be recorded at baseline. Measurements of these lesions are not required, but the presence, absence, or in rare cases unequivocal progression of each should be noted throughout follow up.

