### **3.1 Eligibility Criteria**

3.1.1 Patients must have histologically or cytologically confirmed Stage IV invasive breast cancer. Patients without pathologic or cytologic confirmation of metastatic disease should have unequivocal evidence of metastasis from physical examination or radiologic evaluation.

- 3.1.2 Subjects must have at least one lesion that is not within a previously radiated field that is evaluable on computerized tomography (CT) or magnetic resonance imaging (MRI) scan per RECIST version 1.1. If the subject's only evaluable disease is within a previously radiated field, it must have demonstrated progression since the time of radiation.
- 3.1.3 Participants must have HR positive, HER2-negative breast cancer (ER>1% and/or, PR>1%, HER2-negative per ASCO CAP guidelines, 2013 resulted on the primary tumor and/or a metastatic lesion).
- 3.1.4 Participants must have already received or been intolerant to at least two lines of hormonal therapies (including the adjuvant or metastatic setting) or be appropriate candidates for chemotherapy
- 3.1.5 **Prior chemotherapy:**  
Participants are allowed to have received up to 2 prior lines of chemotherapy in the metastatic setting. If a prior chemotherapy was given for less than 1 cycle, it will not be counted as a prior line. The last dose of chemotherapy must be  $\geq$ 14 days prior to initiation of study therapy. Participants should be adequately recovered from acute toxicities of prior treatment. No prior treatment with eribulin mesylate is allowed.
- 3.1.6 **Prior biologic therapy:** The last dose of biologic or investigational therapy must be  $\geq$ 21 days prior to initiation of study therapy.
- 3.1.7 **Prior hormonal therapy:** Hormonal therapy must have been discontinued  $\geq$ 14 days prior to initiation of study therapy. However, continuation of ovarian suppression is allowed.
- 3.1.8 **Prior radiation therapy:** Participants may have received prior radiation therapy in either the metastatic or early-stage setting. Radiation therapy must be completed  $\geq$ 14 days prior to initiation of study therapy.
- 3.1.9 **Prior targeted therapy:** Targeted therapy must have been discontinued  $\geq$  14 days prior to initiation of study therapy.
- 3.1.10 **Biphosphonates/Denosumab:** Participants on bisphosphonates/denosumab may continue receiving bisphosphonate therapy during study treatment.

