#### 11.1.3.1 Evaluation of Target Lesions

**Complete Response (CR):** Disappearance of all target lesions. Any pathological lymph nodes (whether target or non-target) must have reduction in short axis to <10 mm.

Partial Response (PR): At least a 30% decrease in the sum of the diameters of target lesions, taking as reference the baseline sum diameters.

Progressive Disease (PD): At least a 20% increase in the sum of the diameters of target lesions, taking as reference the smallest sum on study (this includes the baseline sum if that is the smallest on study). In addition to the relative increase of 20%, the sum must also demonstrate an absolute increase of at least 5 mm. (Note: the appearance of one or more new lesions is also considered progressions).

Stable Disease (SD): Neither sufficient shrinkage to qualify for PR nor sufficient increase to qualify for PD, taking as reference the smallest sum diameters while on study.

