#### 11.1.3.2 Evaluation of Non-Target Lesions

Complete Response (CR): Disappearance of all non-target lesions and normalization of tumor marker level. All lymph nodes must be non-pathological in size (<10 mm short axis).

Note: If tumor markers are initially above the upper normal limit, they must normalize for a patient to be considered in complete clinical response.

Non-CR/Non-PD: Persistence of one or more non-target lesion(s) and/or maintenance of tumor marker level above the normal limits.

Progressive Disease (PD): Appearance of one or more new lesions and/or *unequivocal progression* of existing non-target lesions. *Unequivocal progression* should not normally trump target lesion status. It must be representative of overall disease status change, not a single lesion increase.

Although a clear progression of “non-target” lesions only is exceptional, the opinion of the treating physician should prevail in such circumstances, and the progression status should be confirmed at a later time by the review panel (or Principal Investigator).

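### A patient whose only disease is an irradiated lesion that has progressed cannot have a PR, and growth of that lesion counts towards the primary PFS only by judgement

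*Combined protocol and SAP*

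**What the plan says.** Section 3.1.2 requires at least one lesion outside any irradiated field that is "evaluable on computerized tomography (CT) or magnetic resonance imaging (MRI) scan per RECIST version 1.1". It then opens a second route: "If the subject's only evaluable disease is within a previously radiated field, it must have demonstrated progression since the time of radiation".

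Section 11.1.2 notes: "Tumor lesions that are situated in a previously irradiated area are not considered measurable". No exception follows for a lesion that has grown since radiation. The same section draws target lesions only from measurable disease: "All measurable lesions up to a maximum of 2 lesions per organ and 5 lesions in total". All other lesions are non-target, and their measurements need not be recorded.

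Section 11.1.3.1 bases PR on target lesions ("At least a 30% decrease in the sum of the diameters of target lesions") and does the same for size-based progression ("At least a 20% increase in the sum of the diameters of target lesions", with an absolute increase of at least 5 mm). Section 11.1.3.2 makes unequivocal progression of non-target lesions PD, but adds: "It must be representative of overall disease status change, not a single lesion increase". It calls clear progression of non-target lesions alone exceptional, lets the treating physician's opinion prevail, and provides for later confirmation by a review panel or the Principal Investigator.

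**The concern.** At entry, the protocol accepts growth after radiation as showing that the lesion is active disease which can be followed. At follow-up, it withholds from the same lesion the size rules that give RECIST its objectivity.

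The primary endpoint is PFS per RECIST 1.1 in an open-label trial. For these patients, whether and when growth of the qualifying lesion is progression depends on a physician who knows the arm. Confirmation under 11.1.3.2 is not stated to be blinded. Because non-target measurements are not required, a later sensitivity analysis may be unable to recover an objective date. Response is affected too: the lesion can shrink by any amount short of disappearance without being counted.

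**Working it through.** **1. What outcomes are open to such a patient.** Take a patient admitted by the second route of 3.1.2, with no disease outside the field.

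- By 11.1.2 the lesion is not measurable, so it cannot be a target lesion and the patient has none.
- The table in 11.1.3.4 for non-measurable disease allows CR, non-CR/non-PD, not evaluated, or PD (unequivocal progression or a new lesion). PR is not among them.
- Under irRECIST, 11.3.1.3 states that PR does not apply to non-target lesions, and their growth is not PD unless the tumor burden of target lesions rises by 25%. So irRECIST offers no way round.
- Section 13.5 evaluates ORR and CBR in all patients who initiated protocol therapy, so the patient stays in the denominator. CBR is affected as well: 11.1.5 needs SD of at least 27 weeks, while 11.1.3.4 advises against assigning SD to non-target disease.

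**2. Illustration with a 30 mm in-field lesion.**

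| Change | Arithmetic | As target lesion | As non-target lesion |
|---|---|---|---|
| 30 to 38 mm | +8 mm; 8/30 = +26.7% | PD (over 20% and over 5 mm) | Indeterminate: PD only if judged unequivocal |
| 30 to 15 mm | −15/30 = −50% | PR | Non-CR/non-PD |

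**3. Size of the effect on ORR.** The documents give no count of such patients. Assume 5–10% of 88, that is 4.4 to 8.8 patients, and a true ORR of 20%. Assume also that their lesions would otherwise be measurable and that all their responses would be PRs. Reported ORR is then 20% × (1 − 0.05) = 19% to 20% × (1 − 0.10) = 18%.

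**4. Size of the effect on power.** First, the plan's own figure. Section 13.2 states 83% power with 70 events, HR 0.58 and one-sided alpha 0.1. By Schoenfeld's formula:

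Φ(|ln 0.58| × √(70/4) − 1.282) = Φ(0.545 × 4.183 − 1.282) = Φ(0.997) = 84.1%.

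Freedman's formula gives 82.7%. Schoenfeld with the futility stop at Z < 0 at half the information gives 82.6%. The 83% is reproduced.

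Expected events follow from exponential PFS with medians 4.1 and 7.1 months, 44 per arm, uniform accrual over 18 months and 5% dropout at 1 year. At 24 months they are 38.3 + 31.7 = 69.9 (from unrounded values), against the stated 70.

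Now let a share f of PFS events be missed outright (an assumption):

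| f | Expected events at 24 months | Power on 70 × (1 − f) events |
|---|---|---|
| 0 | 69.9 | 84.1% |
| 2% | 68.5 | 83.5% |
| 5% | 66.4 | 82.6% |
| 10% | 62.9 | 81.1% |

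If the analysis waits for 70 events, power at that count is unchanged and only the date moves. Under 13.4 the backstop is 12 months after the last enrolment, month 30 on this accrual. Expected events by then are 77.7 with f = 0 and 77.7 × 0.90 = 70.0 with f = 10%, so 70 stays reachable up to about that share.

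**The case against.** The strongest reply is that nothing here is inconsistent. Section 3.1.2 asks for evaluable disease, and 11.1.1 and 11.1.3.4 make explicit provision for patients with evaluable but non-measurable disease, such as bone lesions or effusions. A patient with only irradiated disease is treated like any of them. Keeping irradiated tissue out of the target sum is also a defensible choice, because post-radiation change can be mistaken for tumor. Both points stand, so a reader who infers that 3.1.2 and 11.1.2 contradict each other goes further than the text allows.

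A reader might also infer that growth of the lesion can never be PD. The documents do not say so. The sentence in 11.1.3.2 against relying on a single lesion follows one about not overriding target-lesion status, which presupposes that target lesions exist. Where the irradiated lesion is the only disease, its growth can fairly be read as a change in overall disease status. The 38 mm example is therefore open, not a definite non-PD. That answers the claim of certainty, but it leaves the date to judgement.

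Finally, the rule is identical in both arms, and missing 10% of events outright is an extreme assumption, since it allows for no later new lesion, unequivocal progression or death. This also stands.

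**Conclusion.** The gap is real and its effect is limited. Patients whose sole evaluable disease is an irradiated lesion that has progressed cannot have a PR under either set of criteria, yet they count in the ORR denominator. Growth of that lesion reaches the primary endpoint only through an open-label judgement of unequivocal progression. New lesions and death remain PFS events.

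The documents do not support a claim that the primary comparison is biased or materially underpowered: the rule does not differ by arm, and the loss of power is about 3 points at the extreme. The ORR shift of 1 to 2 points rests on the assumed 5–10% share, an assumed true ORR of 20%, and the premise that these lesions are otherwise measurable. CR remains possible, and any CRs among the responses would make the shift smaller. What is to be gained is objectivity of progression dates and a fair ORR in a subgroup of unknown size. That is worth a cheap amendment.

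**What to change.** Amend the note in 11.1.2 so that a lesion in a previously irradiated area is non-measurable unless progression of that lesion since radiation has been documented and it otherwise meets the measurability criteria of that section. Record the documentation at baseline. The lesion can then be a target lesion, with an objective progression date and a route to PR.

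The cost is one sentence and one baseline field. There are three limits:

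- Some post-radiation change may be measured as tumor; requiring documented progression reduces this risk but does not remove it.
- Lesions that are non-measurable for another reason, such as bone lesions, are not helped.
- The amended note would also let a progressed irradiated lesion become a target in patients who have disease elsewhere, so its reach is wider than the group admitted by the second route of 3.1.2.

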### 11.1.3 Methods for Evaluation of Disease

All measurements should be taken and recorded in metric notation using a ruler, calipers, or a digital measurement tool. All baseline evaluations should be performed as closely as possible to the beginning of treatment and never more than 4 weeks before the beginning of the treatment.

The same method of assessment and the same technique should be used to characterize each identified and reported lesion at baseline and during follow-up. Imaging-based evaluation is preferred to evaluation by clinical examination unless the lesion(s) being followed cannot be imaged but are assessable by clinical exam.

**Clinical lesions.** Clinical lesions will only be considered measurable when they are superficial (*e.g.*, skin nodules and palpable lymph nodes) and  $\geq 10$  mm in diameter as assessed using calipers (*e.g.*, skin nodules). In the case of skin lesions, documentation by color photography, including a ruler to estimate the size of the lesion, is recommended.

**Chest x-ray.** Lesions on chest x-ray are acceptable as measurable lesions when they are clearly defined and surrounded by aerated lung; however, CT is preferable.

**Conventional CT and MRI.** This guideline has defined measurability of lesions on CT scan based on the assumption that CT thickness is 5mm or less. If CT scans have slice thickness greater than 5 mm, the minimum size of a measurable lesion should be twice the slice thickness. MRI is also acceptable in certain situations (*e.g.* for body scans).

Use of MRI remains a complex issue. MRI has excellent contrast, spatial, and temporal resolution; however, there are many image acquisition variables involved in MRI, which greatly impact image quality, lesion conspicuity, and measurement. Furthermore, the availability of MRI is variable globally. As with CT, if an MRI is performed, the technical specifications of the scanning sequences used should be optimized for the evaluation of the type and site of disease. Furthermore, as with CT, the modality used at follow-up should be the same as was used at baseline and the lesions should be measured/assessed on the same pulse sequence. It is beyond the scope of the RECIST guidelines to prescribe specific MRI pulse sequence parameters for all scanners, body parts, and diseases. Ideally, the same type of scanner should be used and the image acquisition protocol should be followed as closely as possible to prior scans. Body scans should be performed with breath-hold scanning techniques, if possible.

**FDG-PET.** While FDG-PET response assessments need additional study, it is sometimes reasonable to incorporate the use of FDG-PET scanning to complement CT scanning in assessment of progression (particularly possible 'new' disease). New lesions on the basis of FDG-PET imaging can be identified according to the following algorithm:

- (a) Negative FDG-PET at baseline, with a positive FDG-PET at follow-up is a sign of PD based on a new lesion.
- (b) No FDG-PET at baseline and a positive FDG-PET at follow-up: If the positive

FDG-PET at follow-up corresponds to a new site of disease confirmed by CT, this is PD. If the positive FDG-PET at follow-up is not confirmed as a new site of disease on CT, additional follow-up CT scans are needed to determine if there is truly progression occurring at that site (if so, the date of PD will be the date of the initial abnormal FDG-PET scan). If the positive FDG-PET at follow-up corresponds to a pre-existing site of disease on CT that is not progressing on the basis of the anatomic images, this is not PD.

(c) FDG-PET may be used to upgrade a response to a CR in a manner similar to a biopsy in cases where a residual radiographic abnormality is thought to represent fibrosis or scarring. The use of FDG-PET in this circumstance should be prospectively described in the protocol and supported by disease-specific medical literature for the indication. However, it must be acknowledged that both approaches may lead to false positive CR due to limitations of FDG-PET and biopsy resolution/sensitivity.

Note: A 'positive' FDG-PET scan lesion means one which is FDG avid with an uptake greater than twice that of the surrounding tissue on the attenuation corrected image.

**PET-CT.** At present, the low dose or attenuation correction CT portion of a combined PET-CT is not always of optimal diagnostic CT quality for use with RECIST measurements. However, if the site can document that the CT performed as part of a PET-CT is of identical diagnostic quality to a diagnostic CT (with IV and oral contrast), then the CT portion of the PET-CT can be used for RECIST measurements and can be used interchangeably with conventional CT in accurately measuring cancer lesions over time. Note, however, that the PET portion of the CT introduces additional data which may bias an investigator if it is not routinely or serially performed.

**MIBG (meta-iodobenzylguanidine).** The following is recommended, to assure high quality images are obtained.

Patient preparation: Iodides, usually SSKI (saturated solution of potassium iodide), are administered to reduce thyroidal accumulation of free radioiodine, preferably beginning the day prior to injection and continuing for 3 additional days (4 days total). For infants and children, one drop t.i.d. is sufficient, for adolescents 2 drops t.i.d., and for adults 3 drops t.i.d. Participants and/or parents are asked about exposure to potential interfering agents. If none is noted, an indwelling intravenous line is established. The dose of MIBG is administered by slow intravenous injection over 90 seconds.

Images from the head to the distal lower extremities should be obtained.

I-123MIBG scintigraphy is performed to obtain both planar and tomographic images.

Planar: Anterior and posterior views from the top of the head to the proximal lower extremities are obtained for 10 minutes at 24 hours and occasionally at 48 hours

following injection of 10 mCi/1.7 square meters of body surface area (~150  $\mu$ Ci/kg, maximum 10 mCi). Anterior views of the distal lower extremities are adequate. A large field of view dual head gamma camera with low energy collimators is preferred.

**SPECT:** Most participants receiving I-123 MIBG also undergo SPECT at 24 hours, using a single or multi-headed camera with a low energy collimator. The camera is rotated through 360 degrees, 120 projections at 25 seconds per stop. Data are reconstructed using filtered back projections with a Butterworth filter and a cut off frequency of 0.2-0.5. SPECT/CT may be performed at institutions with this capacity.

**Ultrasound.** Ultrasound is not useful in assessment of lesion size and should not be used as a method of measurement. Ultrasound examinations cannot be reproduced in their entirety for independent review at a later date and, because they are operator dependent, it cannot be guaranteed that the same technique and measurements will be taken from one assessment to the next. If new lesions are identified by ultrasound in the course of the study, confirmation by CT or MRI is advised. If there is concern about radiation exposure from CT, MRI may be used instead of CT in selected instances.

**Endoscopy, Laparoscopy.** The utilization of these techniques for objective tumor evaluation is not advised. However, such techniques may be useful to confirm complete pathological response when biopsies are obtained or to determine relapse in trials where recurrence following complete response (CR) or surgical resection is an endpoint.

**Tumor markers.** Tumor markers alone cannot be used to assess response. If markers are initially above the upper normal limit, they must normalize for a participant to be considered in complete clinical response. Specific guidelines for both CA-125 response (in recurrent ovarian cancer) and PSA response (in recurrent prostate cancer) have been published [JNCI 96:487-488, 2004; J Clin Oncol 17, 3461-3467, 1999; J Clin Oncol 26:1148-1159, 2008]. In addition, the Gynecologic Cancer Intergroup has developed CA-125 progression criteria which are to be integrated with objective tumor assessment for use in first-line trials in ovarian cancer [JNCI 92:1534-1535, 2000].

**Cytology, Histology.** These techniques can be used to differentiate between partial responses (PR) and complete responses (CR) in rare cases (e.g., residual lesions in tumor types, such as germ cell tumors, where known residual benign tumors can remain).

The cytological confirmation of the neoplastic origin of any effusion that appears or worsens during treatment when the measurable tumor has met criteria for response or stable disease is mandatory to differentiate between response or stable disease (an effusion may be a side effect of the treatment) and progressive disease.

